2 SYNOPSIS

NAME OF SPONSOR: Amgen	PROTOCOL No.: 20130109
NAME OF STUDY TREATMENT: ABP 798	
TITLE OF STUDY: A Randomized, Double-blind Study Evaluating the Efficacy, Safety, and Immunogenicity of ABP 798 Compared with Rituximab in Subjects with CD20 Positive B-cell Non-Hodgkin Lymphoma (NHL)	
STUDY CENTERS: Approximately 150 sites in Europe, North America, Latin America , and Asia Pacific	
STUDY PERIOD: Approximately 250 subjects will be randomized in a 1:1 ratio to receive ABP 798 or rituximab (Rituxan®). The clinical study will be completed when the last subject completes the week 28 visit or withdraws early from the study.	PHASE OF DEVELOPMENT: Phase 3
PLANNED STUDY DATES: The study consists of a screening period of up to 4 weeks and a treatment period of 28 weeks, for a total of up to 32 weeks. The expected enrollment duration is approximately 24 months.	
OBJECTIVES: Primary Objective: The primary objective for this study is to evaluate the efficacy of ABP 798 compared with rituximab. Secondary Objective(s): The secondary objective is to assess the pharmacokinetics (PK), pharmacodynamics, safety, tolerability, and immunogenicity of ABP 798 compared with rituximab.	
STUDY DESIGN AND METHODOLOGY: This is a randomized, double-blind study in adult subjects with Grade 1, 2, or 3a follicular B-cell non-Hodgkin lymphoma (NHL) and low tumor burden. Approximately 250 subjects (125 per treatment group) will be randomized (1:1) to receive investigational product (IP) (ABP 798 or rituximab) at a dose of 375 mg/m ² administered as an intravenous (IV) infusion once weekly for 4 weeks followed by dosing at weeks 12 and 20. Tumor assessment will be performed at baseline and weeks 12 and 28. Subjects will be stratified by geographic area and age (> 60 vs ≤ 60 years). A subject will remain on study until week 28. Subjects who discontinue IP before week 20 will be followed for 8 weeks after the last dose of IP and then complete the end-of-study visit. An independent data monitoring committee (DMC) will evaluate the safety data throughout the study, including an initial safety review after the first 12 subjects have received at least 2 doses of IP.	
STUDY POPULATION AND MAIN CRITERIA FOR INCLUSION/EXCLUSION: Inclusion Criteria: Subjects cannot be randomized before all inclusion criteria (including test results) are confirmed. 
1. Males and females 18 years of age and older2. Histological confirmed (by lymph node or extranodal region biopsy), Grade 1, 2, or 3a follicular B-cell NHL expressing CD20 within 12 months before randomization3. Stage 2, 3, or 4 (per Cotswold's Modification of Ann Arbor Staging System; Appendix 3) with measurable disease (per International Working Group)
• subjects must have a baseline scan (computed tomography [CT]) of the neck (if palpable lymph node > 1.0 cm), chest, abdomen, and pelvis to assess disease burden within 6 weeks before randomization• subjects must have had a baseline bone marrow biopsy within 12 months before randomization. Previously confirmed positive bone marrow involvement does not need to be repeated for purposes of screening.4. Low tumor burden based on the Groupe d'Etudes des Lymphomes Folliculaires (GELF) criteria (Appendix 4)
• largest nodal or extranodal mass ≤ 7 cm• no more than 3 nodal sites with diameter > 3 cm• no splenomegaly > 16 cm by CT scan and no symptomatic splenomegaly• no significant pleural or peritoneal serous effusions by CT• lactate dehydrogenase ≤ upper limit of normal (ULN)	

- no B symptoms (night sweats, fever [temperature > 38°C], weight loss > 10% in the previous 6 months)
- 5. Eastern Cooperative Oncology Group (ECOG) performance status score 0 or 1
- 6. Blood counts:
 - absolute neutrophil count (ANC) $\geq 1.5 \times 10^9/L$ (1,500/ μ L)
 - lymphocytes < 1.5 x the ULN
 - platelets $\geq 100 \times 10^9/L$ (100,000/ μ L)
 - hemoglobin ≥ 10.0 g/dL
- 7. Adequate hepatic function as defined by:
 - total bilirubin < 1.5 x the ULN
 - aspartate aminotransferase (AST) and alanine aminotransferase (ALT) < 2 x ULN
 - Subjects with an elevated unconjugated bilirubin (Gilbert's syndrome) will be eligible if hepatic enzymes and function are otherwise within normal limits (ie, AST, ALT, and alkaline phosphatase are within normal limits) and there is no evidence of hemolysis.
- 8. Adequate renal function as defined by creatinine < 1.5 x ULN or estimated creatinine clearance ≥ 50 mL/min calculated by the Cockcroft-Gault method
- 9. Subjects must sign an Institutional Review Board/Independent Ethics Committee-approved informed consent form before any study specific procedures.

Exclusion Criteria:

If any of the following apply, the subject **MUST NOT** enter the study:

1. Diffuse large cell component and/or Grade 3b follicular NHL
2. History or known presence of central nervous system metastases
3. Palliative radiotherapy within 3 months before randomization
4. Malignancy other than NHL within 5 years (except treated in-situ cervical cancer, or squamous or basal cell carcinoma of the skin)
5. Major surgical procedure within 4 weeks before randomization or planned major surgical procedure during the treatment phase
6. Any of the following in the 6 months before randomization:
 - clinically significant cardiovascular disease (including myocardial infarction, unstable angina, symptomatic congestive heart failure [New York Heart Association \geq Class III], serious uncontrolled cardiac arrhythmia); peripheral vascular disease, cerebrovascular accident, or transient ischemic attack
7. Medically uncontrolled hypertension or systolic blood pressure > 160 mmHg or diastolic blood pressure > 100 mmHg
8. Known active or history of active tuberculosis (TB)
9. Positive for hepatitis B surface antigen, hepatitis B core antibody, or hepatitis C virus antibody at screening
10. Known to be human immunodeficiency virus positive
11. Recent infection requiring a course of systemic anti-infective agents that was completed ≤ 7 days before randomization (with the exception of uncomplicated urinary tract infection)
12. Other investigational procedures **that can impact the study data, results, or patient safety** while participating in this study are excluded; **participation in observational studies is allowed.**
13. Subject is currently enrolled in or has not yet completed at least 30 days or 5 half-lives (whichever is longer) since ending other investigational device or drug study(s), including vaccines, or subject is receiving other investigational agent(s)
14. Previous use of either commercially available or investigational chemotherapy, biological, or immunological therapy for NHL (including rituximab or biosimilar rituximab, or other anti-CD20 treatments)
15. Systemic corticosteroid use **within** 3 months before randomization (inhaled are allowable)
16. Live vaccines within 28 days prior to the first dose of IP
17. History of neurologic symptoms suggestive of central nervous system demyelinating disease

18. Woman of childbearing potential who is pregnant or is breastfeeding
19. Woman of childbearing potential who does not consent to use highly effective methods of birth control (eg, true abstinence, sterilization, birth control pills, Depo Provera injections, or contraceptive implants) during treatment and for an additional 12 months after the last administration of the protocol specified-treatment
20. Man with a partner of childbearing potential who does not consent to use highly effective methods of birth control (eg, true abstinence, vasectomy, or a condom in combination with hormonal birth control or barrier methods used by the woman) during treatment and for an additional 12 months after the last administration of the protocol specified treatment
21. Subject has known sensitivity to any of the products to be administered during the study, including mammalian cell derived drug products
22. Subject previously has been randomized in this study
23. Subject likely to not be available to complete all protocol-required study visits or procedures
24. History or evidence of any other clinically significant disorder, condition or disease (with the exception of those outlined above) that, in the opinion of the Investigator or Amgen physician, if consulted, would pose a risk to subject safety or interfere with the study evaluation, procedures or completion

NUMBER OF SUBJECTS: Approximately 250 subjects will be randomized in a 1:1 ratio to receive ABP 798 or rituximab.

STUDY TREATMENT(S):

Test Product, Dose and Mode of Administration:

ABP 798 at a dose of 375 mg/m² administered as an IV infusion weekly for 4 weeks followed by dosing at weeks 12 and 20.

Reference Therapy, Dose and Mode of Administration:

Rituximab at a dose of 375 mg/m² administered as an IV infusion weekly for 4 weeks followed by dosing at weeks 12 and 20.

DURATION OF TREATMENT: The study includes a screening period of up to 4 weeks. Subjects will receive IP at day 1 (visit 1) and weeks 2 (visit 2), 3 (visit 3), 4 (visit 4), 12 (visit 5), and 20 (visit 6) and will have an end-of-study visit at week 28. Individual total study duration will be 32 weeks.

STUDY EVALUATIONS:

Primary Efficacy Criterion:

- Risk difference of ORR by week 28

Secondary Efficacy Criteria:

- Risk difference of ORR at week 12

Pharmacokinetic and Pharmacodynamic Criteria:

- Percentage of subjects with complete depletion of CD19+ cell count from baseline to study day 8 and total IgG and IgM antibody levels
- Serum concentrations at predose and immediately after the end of infusion at week 12

Safety Criteria:

- Treatment-emergent adverse events (AEs) and serious AEs (SAEs)
- Clinically significant changes in laboratory values and vital signs
- Incidence of antidrug antibodies
- On study progression-free survival (PFS)
- On study overall survival (OS)

STATISTICAL METHODS:

Clinical equivalence of the primary endpoint will be demonstrated by first assessing non-inferiority by comparing the 1-sided 95% lower confidence interval (CI) limit of the RD of ORR by week 28 between ABP 798 and rituximab with a -15% margin. If the test of non-inferiority is successful, then the study will sequentially assess non-superiority by comparing the 1-sided 95% upper CI limit of the RD of ORR by week 28 with a 35.5% margin. Additionally, a 2-sided 95% CI will be calculated and evaluated against a symmetrical margin of 15% for noninferiority and nonsuperiority. The CIs for RD will be estimated using a generalized linear model adjusted for stratification factors. Analyses of efficacy endpoints will be conducted on the full analysis set (consisting of all randomized subjects) according to randomized treatment.

In addition, categorical variables will be summarized using the number and percentage of subjects falling into each category. Continuous variables will be summarized using mean, standard error or standard deviation, median, minimum, maximum, and number of subjects with observations.

Pharmacokinetics endpoints will be summarized as point estimates of the geometric mean ratio and 90% CIs of test (ABP 798)-to-reference (rituximab). The pharmacodynamic endpoint of percentage of subjects with complete depletion of CD19+ cell count from baseline to study day 8 will be summarized descriptively. Pharmacokinetics and pharmacodynamic endpoints will be conducted on safety analysis set (consisting of subjects receiving at least 1 dose of IP) according to actual treatment received.

Safety endpoints will be summarized descriptively as well. Subgroup analyses (by gender, race, and stratification factors as appropriate) may be presented. Safety will be assessed in the safety analysis set with treatment assignment based on actual treatment received. All verbatim terms for any reported AEs will be coded to the appropriate system organ class and preferred term according to the current version of the Medical Dictionary for Regulatory Activities dictionary, and graded by the Investigator for severity as per Common Toxicity Criteria for Adverse Events version 4.03. The number and percentage of subjects reporting AEs (all, serious, related, and deaths), and developing antidrug antibodies will be tabulated by treatment. Vital signs and laboratory data will also be summarized descriptively by visit and treatment. The safety endpoints of PFS and OS will be analyzed including all events up to the time of the last subject's end-of-study visit. Median PFS and OS time and survival curves may also be estimated using Kaplan-Meier methods. Descriptive 1-sided 95% and 97.5% CIs on the hazard ratios of PFS and OS will be estimated based on Cox models, stratified by stratification factors.

Independent safety reviews will be performed by the DMC periodically throughout the study, including an initial safety review after the first 12 subjects have received at least 2 doses of IP. Blinded study data will also be monitored on an ongoing basis by the blinded clinical study team to ensure subjects' safety.

DATE AND VERSION: 5.0, 17 July 2017

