9.1 Screening

Unless otherwise stated, the following assessments/procedures will be performed within 28 days before randomization. Assessments/procedures performed as routine standard of care, prior to the subject signing informed consent, and according to the criteria outlined in [Section 10](#), can be used for screening purposes as long as the assessments/procedures were performed within 28 days before randomization (except for bone marrow biopsy **and CT scan**).

- informed consent form
- medical history, including history of NHL
- physical examination, including evaluation of body systems
- vital signs (systolic and diastolic blood pressure, pulse, respiration rate, and temperature)
- standard 12-lead electrocardiogram (ECG)
- ECOG performance status
- baseline CT of the neck (if palpable lymph node >1.0 cm), chest, abdomen, and pelvis **within 6 weeks before randomization**
- bone marrow biopsy within 12 months before randomization. Previously confirmed positive bone marrow involvement does not need to be repeated for purposes of screening
- clinical laboratory testing, including serology, serum chemistry, and hematology
- serum or urine pregnancy test for women of childbearing potential

At the screening assessment, all concomitant medications from 3 months before the planned start of study treatment will be recorded. Any AEs occurring during the screening period will be recorded as medical history; any SAEs will be recorded using the eCRF. SAEs will be reported as outlined in [Section 11.2.2](#). After screening but within 8 days before starting treatment, for eligible subjects the Investigator will contact the IXRS for randomization. **(Height and weight are required for IXRS randomization and must be collected within 8 days of visit 1).**

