9.2 Baseline (Day 1, first day of administration of investigational product)

Day 1 will be defined as the first day of administration of IP. After subjects are confirmed to meet the entry criteria ([Section 8.4](#)), the Investigator (or designee) will contact the IXRS to randomize the subject centrally to receive blinded IP (ABP 798 or rituximab) within 8 days before the baseline visit. The following assessments/procedures will be performed before treatment:

- physical examination, including evaluation of body systems and **baseline** height and weight; **baseline height and weight will be measured within 8 days of visit 1 to allow use in randomization of subjects within 8 days of visit 1**
- vital signs (systolic and diastolic blood pressure, pulse, respiration rate, and temperature)
- clinical disease assessment
- clinical laboratory testing, including serum chemistry and hematology (can be performed up to 3 days before baseline [day 1])
- collection of samples for pretreatment PK samples, pretreatment antidrug antibodies, pretreatment samples for CD19+ cell count, and IgG and IgM levels

Any changes in concomitant medications since the last assessment will be recorded.

Any pretreatment AEs will be recorded as medical history; any pretreatment SAEs will be recorded using the eCRF. SAEs will be reported as outlined in [Section 11.2.2](#).

After completion of pretreatment procedures and premedications, ABP 798 or rituximab will be administered as an IV infusion in a double-blinded fashion. The dose calculation for ABP 798 or rituximab will be based on the height and weight obtained **within 8 days of visit 1**. Starting at the time of first treatment, all AEs, including increases in severity or frequency of pre-existing conditions, will be recorded in the eCRF.

All subjects will be monitored for hypersensitivity reactions to IP by assessment of vital signs (systolic and diastolic blood pressure, pulse, respiration rate, and temperature) at the time points outlined in [Section 8.5.1](#) (every 60 minutes during IP infusion, at the end

of the IV infusion, and approximately 60 minutes after the end of the IV infusion).

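### The only required pregnancy test can be 28 to 36 days old at the first infusion, and the contraception criterion for women does not cover that interval

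*Protocol*

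**What the plan says.** Criterion 18 (Protocol Synopsis and Section 8.4.2) excludes a "Woman of childbearing potential who is pregnant or is breastfeeding". Criterion 19 excludes a woman of childbearing potential who does not agree to highly effective contraception "during treatment and for an additional 12 months after the last administration of the protocol specified-treatment".

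Section 9.1 lists a "serum or urine pregnancy test for women of childbearing potential" among the screening procedures and states that, unless otherwise noted, "the following assessments/procedures will be performed within 28 days before randomization". Routine-care results obtained before consent may be used within the same window. The stated exemption from that window is "except for bone marrow biopsy and CT scan", so the pregnancy test stays at 28 days.

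On randomization, Section 9.1 says: "After screening but within 8 days before starting treatment, for eligible subjects the Investigator will contact the IXRS for randomization". Section 9.2 likewise places it "within 8 days before the baseline visit".

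The pregnancy row of Table 1 has one mark, in the screening column. Footnote n says who is tested and where, and adds no second time point. Section 10.2 gives the method only. The procedure lists for day 1, visits 2 to 6 and end of study (Sections 9.2 to 9.6) contain no pregnancy test, and the laboratory panel in Section 10.6 does not include one.

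The Synopsis and Section 8.3 give a screening period of up to 4 weeks and a total study duration of 32 weeks.

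**The concern.** The protocol treats exposure in pregnancy as serious. It is an exclusion, a reason for removal (Section 8.4.3.1) and a matter for mandatory reporting (Section 11.4), and contraception must continue for 12 months after the last dose. The check behind the exclusion is nevertheless dated from randomization, while the hazard begins at the first infusion.

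Two safeguards could cover the time between the test and day 1: a test close to dosing, or a contraception commitment that starts no later than the test. The plan requires neither. A site that follows every listed procedure could therefore randomize and dose a woman who conceived after her screening test, and no required step would reveal it. What is at stake is fetal safety. The efficacy analysis is not affected.

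**Working it through.** The plan states no figure for the interval from test to first dose, so it is built from the protocol's own windows.

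**Inputs**
- Latest permitted age of the test at randomization: 28 days (Section 9.1).
- Longest interval from randomization to day 1: 8 days (Sections 9.1 and 9.2).
- Stated screening period: up to 4 weeks (Synopsis, Section 8.3). The Table 1 screening column gives 28 days without naming an anchor date.
- Stated treatment period: 28 weeks; stated total: up to 32 weeks (Synopsis).

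**Longest gap on the wording of Sections 9.1 and 9.2**

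Gap = (test to randomization) + (randomization to day 1) = 28 + 8 = 36 days.

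**Longest gap if screening runs to day 1**

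Gap = 4 × 7 = 28 days.

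**Do the two readings agree?**
- Stated total: 4 + 28 = 32 weeks.
- With 36 days before treatment: 36 / 7 = 5.14 weeks, and 5.14 + 28 = 33.14 weeks.

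The windows in Sections 9.1 and 9.2 therefore allow more time before dosing than the Synopsis and Section 8.3 do. The range is 28 to 36 days, with 36 on the more explicit text. Neither reading includes a required repeat before the first dose.

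**Contraception over the same interval**

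Criterion 19 covers treatment and the 12 months after the last dose. The interval from the test to day 1, 28 to 36 days at most, lies outside that wording.

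**How other checks before dosing are dated**
- Day-1 chemistry and hematology: up to 3 days before day 1 (Section 9.2, Table 1 footnote m).
- Height and weight: within 8 days of visit 1 (Sections 8.5.1, 9.1 and 9.2).
- Live vaccines, criterion 16: counted back 28 days from the first dose.
- Pregnancy test: counted back from randomization.

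The protocol already anchors several items to dosing. The pregnancy test is not one of them.

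**The case against.** Several points on the other side stand.

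- Repeat laboratory testing is allowed at the investigator's discretion (Table 1 footnote l, Section 10.6). A repeat before dosing is therefore possible, but it is not required.
- 36 days is a permitted maximum, not a typical interval, and the 4-week reading gives 28.
- The 8-day rule for height and weight exists because those values feed the dose calculation and the randomization system. It sets no standard for pregnancy testing. It shows only that a window anchored to dosing is already workable at sites.
- The share of women of childbearing potential is not stated. Section 6.1 gives a median age at diagnosis of 60, which suggests a minority.
- The consent form is not among the documents, so its wording on contraception cannot be checked.

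Three stronger readings are tempting, and the documents do not support them.

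- A reader might infer that a woman who conceives after the test can be dosed while still satisfying all entry criteria. She cannot. Criterion 18 describes a state, not a test result, and Section 10.2 repeats that pregnant subjects are excluded. She would breach the criterion; the gap is in verification.
- A reader might extend the point to criterion 20. For a male subject, conception by his partner before day 1 precedes any exposure of his to study drug, so it is not the same hazard.
- A reader might count the age of the single result up to the week-20 dose. From day 1 onward criterion 19 does require contraception, so that longer interval is a different question from the uncovered one before dosing.

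**Conclusion.** The point holds as a verification gap. The one required pregnancy test can be 36 days old at the first infusion on the wording of Sections 9.1 and 9.2, or 28 days if the 4-week screening period runs to day 1. No repeat is required, and criterion 19 does not reach back over the interval. A conception in that time would breach criterion 18 without any required check detecting it.

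This rests on the text of the protocol alone and assumes that sites use the full windows and do not test again by choice. The number of women exposed to the gap cannot be estimated from the documents. Likelihood is probably low, but the possible harm is serious and the correction is cheap, so the gap should be closed. The conflict between the 28 + 8 days and the 4-week and 32-week statements needs resolving in any case.

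**What to change.** Reconcile the screening and duration statements (Synopsis, Section 8.3), criteria 18 and 19 (Synopsis, Section 8.4.2), the pregnancy row and footnote n of Table 1, and Sections 9.1 and 9.2, so that:

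1. the check of criterion 18 is anchored to the first dose, as is already done for height and weight and for day-1 chemistry and hematology;
2. criterion 19 also covers the interval from the test to the first dose, because even a late test cannot exclude a very recent conception;
3. the screening window, the randomization window and the stated study duration agree.

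The sponsor should set the exact test window and the start date of the contraception commitment. Editing the Synopsis alone would leave the gap open, since the same wording stands in the body of the protocol.

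**Cost.** The change is amendment wording; dosing and analysis are untouched. Some sites would have to test later or repeat a local urine test. There is one further downside: if a single test is simply moved later, the screening CT, allowed up to 6 weeks before randomization, is more likely to precede any pregnancy test. The current text does not put the test before the CT either, so the sponsor should weigh this when choosing between moving the test and repeating it.
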